# Postdose of spirometry may be used for imputation			
The analysis visit windows will be applied using the following rules for both scheduled and unscheduled visits:			
1. If no numerical measurement is available within a visit window, the measurement will be considered			

Table 11-4 Analysis Visit Windows for Safety and Efficacy Assessments			
Assessment	Visit^a	Target Study Day^b	Analysis Visit Window (in study days)
			
missing for the visit.
 
2. If there is more than 1 numerical measurement available within the same visit window, use the following rules:
 
a. For efficacy parameters: if there are multiple measurements within a visit window, the measurement at the scheduled visit will be used. Otherwise,
 
i. If there are no measurements at the scheduled visit, then the measurement closest to the target day will be used; or
 
ii. If there are multiple measurements with the same distance to the target day, the latest measurement will be used.
 
b. For safety parameters: if there are multiple measurements within a visit window,
 
i. The measurement closest to the target day will be used; or
 
ii. If there are multiple measurements within the same distance from the target day, the latest measurement will be used.
 
iii. For tables of extreme lab measurements based on ULN or LLN, convert the lab measurements into \timesULN or \timesLLN first, and then select the extreme measurement.
 
Derived Variables:
 
1. Age (in years) at first dose date
 
Obtain age at screening (in days) in yy mm format (e.g., 24 years, 6 months) from screening vital signs page, and add 0.5 month to convert to days.
 
Obtain screening date from Date of Visit (DOV) page.
 
Then age (in years) at first dose date = integer part of $\{[(\text{first dose date}-\text{screening date}) \text{ in days} + \text{age at screening (in days)}]/365.25\}$.
 
Correspondingly, age (in months) at first dose date = integer part of $12 * \{[(\text{first dose date}-\text{screening date}) \text{ in days} + \text{age at screening (in days)}]/365.25\}$.
 
2. Age (in years) at post-baseline visit (for use in calculation of percent predicted spirometry variables)
 
Age (in years) at post-baseline visit = $[(\text{post-baseline visit date} - \text{screening date}) \text{ in days} + \text{age at screening (in days)}]/365.25$
 
3. Missing First Dose Date or Last Dose Date
 
If the first dose date is missing, use Day 1 visit date.
 
If the last dose date is missing at final analysis, use maximum of Early Treatment Termination (ETT) visit date and last study drug administration date from EX SDTM domain (excluding PK dosing dates). When a subject is lost to follow up without ETT, impute the last dose date as the last treatment period visit date.
 
4. Missing Date for Drug Interruption
 
If the dates for drug interruption are completely missing or partially missing and it cannot be determined in which period the interruption occurred, then assume the interruption occurred during the Treatment Period (Period 1) for 1 day.
 
5. Sweat Chloride:
 
The qualified left arm and right arm SWCL assessments on Day 1 with end date/time for a given arm up to 30 minutes after first dose time will be considered for baseline. If Day 1 value is unavailable or invalid, screening value will qualify as baseline.

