^e Randomization may occur on the previous day (Day -1) after all inclusion and exclusion criteria and criteria for entry into the Treatment Period (see footnote d) have been confirmed.

^f On days of scheduled visits, the in-clinic dose of study drug will be given in the morning, at least 6 hours apart from any other scheduled dose and after all predose assessments are complete. The last dose of VX-659 in Part 2 Period 1 will be the morning dose on the Day 29 Visit. The last dose of TEZ/IVA in Part 2 Period 2 will be the morning dose on the Day 57 Visit. Refer to Section 9.7 for details.

^g CFTR genotyping will be performed for all subjects. If the screening CFTR genotype result is not received before randomization, a previous CFTR genotype laboratory report may be used to establish eligibility (see inclusion criterion 6).

^h Weight and height will be measured with shoes off.

ⁱ Complete and abbreviated PEs are described in Section 11.7.3. Symptom-directed PEs can be done at any time at the discretion of the investigator or healthcare provider.

^j Vital signs and pulse oximetry will be collected after the subject has been seated for at least 5 minutes.

Table 3-2 Study VX16-659-101 Part 2 (Subjects with F/F genotype): Schedule of Assessments

Event/Assessment ^a	Screening Period	Run-in (4 weeks)		Treatment Period (8 weeks)					ETT Visit ^b	Safety Follow-up 28 (± 7) Days After Last Dose ^c
				Period 1 (4 weeks) ^d		Period 2 (4 weeks)				
	Screening Visit Days -56 to -29	Day -28 (± 1 day)	Day -14 (Days -15 to -3)	Day 1	Day 15 (± 2 days)	Day 29 (± 2 days)	Day 43 (± 3 days)	Day 57 (± 3 days)		
Pulse oximetry ^j	X	X		X	X	X	X	X	X	X
Standard 12-lead ECG ^k	X	X		X	X	X	X	X	X	X
Sweat chloride ^{l,o}	X		X	X	X	X	X	X	X	
Spirometry ^m	X		X	X	X	X	X	X	X	X
CFQ-R ^{n,o}				X	X	X	X	X		
Urinalysis ^o	X	X		X	X	X	X	X	X	X
Pregnancy test (all females of childbearing potential)	Serum	Urine		Urine		Urine		Urine	Serum	Serum
FSH ^p	X									
G6PD activity test ^q	X									
Serum chemistry and hematology ^o	X	X		X	X	X	X	X	X	X
Coagulation ^o	X	X		X	X	X			X	X

^k Standard 12-lead ECGs will be performed after the subject has been rested for at least 5 minutes. On Day 1 and 15 Visits, ECGs will be collected before dosing and 5 hours (± 1 hour) after dosing. At other visits, ECGs will be collected before dosing (as applicable). ECGs collected on the Day 1 Visit before dosing will be performed in triplicate.

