9.1.2 Run-in Period (Part 2)

The Run-in Period will have a total duration of 4 weeks and is designed to establish a reliable on-treatment (TEZ/IVA) baseline for the Treatment Period. The first dose of TEZ/IVA will be administered in the morning at the Day -28 Visit. The last dose of IVA within the Run-in Period will be administered in the evening of Day -1 (1 day before the Day 1 Visit).

Study eligibility for Part 2 subjects will be confirmed before the first dose of TEZ/IVA in the Run-in Period (on the Day -28 Visit).

Study visits during the Run-in Period will occur as shown in [Table 3-2](#). All visits will occur within the windows specified.

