9.3 Rationale for Study Design and Study Drug Regimens

9.3.1 Study Design

Stratification of Randomization

The extent of response to CFTR modulator treatment may depend on the subject's ppFEV₁ value (an index of disease severity) before the start of study drug dosing. Therefore, randomization in all parts will be stratified by pretreatment ppFEV₁ values, defined as the last ppFEV₁ measurement before treatment with VX-659. For Parts 1 and 3, this value is determined at screening, except for those subjects who require a Stratification Visit, in which case the value is determined at that visit. For Part 2, the pretreatment ppFEV₁ value is determined at the Day -14 Visit during the Run-In Period.

Control Treatments

Part 1 and Part 3: Efficacy has not been demonstrated for a corrector, potentiator, or any corrector/potentiator combination in subjects with F/MF genotypes. A Phase 3 study of TEZ/IVA in subjects with F/MF genotypes (Study VX14-661-107) was terminated following a planned interim futility analysis, which showed that the combination of TEZ/IVA did not result in a prespecified improvement in ppFEV₁. Because there is no effective treatment for this population, a placebo arm will be included as the control in Part 1 and Part 3.

Part 2: A Phase 3 study of TEZ/IVA (Study VX14-661-106) demonstrated a clinically meaningful benefit in subjects with the F/F genotype¹⁶; therefore, TEZ/IVA is the active control.

Run-in Period

Part 2 will have a 4-week run-in period to establish a reliable on-treatment (TEZ/IVA) baseline for comparison to Period 1, when subjects will additionally receive VX-659 or placebo.

Period 2

Part 1 and Part 2 include a second dosing period (Period 2), during which subjects will be administered TEZ/IVA. In Part 1, Period 2 is 4 days and is included to enable a more thorough evaluation of VX-659 exposure-response relationships by conducting PK and PD assessments during the VX-659 washout. In Part 2, Period 2 is 4 weeks to enable an assessment of PD and efficacy endpoints after VX-659 is washed out.

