The 4-week treatment duration for the TC is based on previous experience with CF correctors and potentiators in clinical studies of subjects with CF. In previous studies of TEZ and IVA, PD effects were observed within 4 weeks of treatment. In Study VX06-770-101, treatment with IVA for 4 weeks resulted in statistically significant within-group changes from baseline in ppFEV₁ as well as a trend toward clinically meaningful improvements in the respiratory domain of the CFQ-R; differences in biomarkers of CFTR activity (sweat chloride) between IVA and placebo groups were also demonstrated. Furthermore, in Study VX11-661-101 dose-dependent improvements in ppFEV₁ were observed for TEZ/IVA after 4 weeks of treatment, with the 2 highest dose groups showing statistically significant improvement in lung function versus placebo.¹⁷ In both studies, improvements in sweat chloride and ppFEV₁ were observed during the first week of dosing, with most of the effect observed within 14 days. Given the increased in vitro response of the TC relative to TEZ/IVA, it is expected that a 4-week treatment duration will be sufficient to observe differences between treatment arms with respect to efficacy and PD endpoints.

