12.3.1 General Considerations

Continuous variables will be summarized using the following descriptive summary statistics: the number of subjects (n), mean, SD, SE, median, minimum value, and maximum value. The precision of the measurement for each continuous variable will be specified in the SAP. Unless otherwise specified, minimum and maximum values will be reported with the same precision as the units of the raw data. The mean, median, SD, and SE will be reported to 1 additional decimal place. Any values that require a transformation to standard units (metric or International System [SI]) will be converted with the appropriate precision.

Categorical variables will be summarized using counts and percentages. Percentages will be presented to 1 decimal place.

The **baseline** value, unless otherwise specified, will be defined as the most recent non-missing measurement (scheduled or unscheduled) collected before the first dose of study drug in the Treatment Period (i.e., the Day 1 Visit). For ECG, baseline will be defined as the most recent pretreatment measurement (or the average of triplicate measurements, if the most recent pretreatment measurement is obtained in triplicate) before the first dose of study drug in Period 1 (i.e., the Day 1 visit).

Absolute change from baseline will be calculated as postbaseline value – baseline value.

Relative change from baseline will be calculated as (postbaseline value – baseline value)/baseline value.

The Treatment-emergent (TE) Period will include the time from the first dose in Period 1 to the Safety Follow-up Visit or 28 days after the last dose of the study drug for subjects who do not complete the Safety Follow-up Visit. Only data collected up to the end of study for a subject will be included in the analysis. An additional TE period related to the Run-in Period for Part 2 will be defined in the SAP, as appropriate.

There will be no multiplicity adjustment for performing multiple hypothesis tests.

The rules for handling missing data due to treatment or study discontinuation will be described in the SAP.

All data will be summarized for each part, separately, unless specified otherwise.

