8 STATISTICAL ANALYSIS

8.1 General Considerations

The analysis will be performed for each part, and presented by treatment group and overall, for the Treatment Period, unless specified otherwise. The treatment groups are defined as follows:

- Part 1: *F508del*/MF genotype group
 - Placebo, TC-low, TC-mid, and TC-high.
- Part 2: *F508del*/*F508del* genotype group
 - TEZ/IVA and TC-high.
- Part 3: *F508del*/MF genotype group
 - Placebo and TC2-high.

The Schedule of Assessments is provided in [Appendix A](#). The precision standards for reporting safety and efficacy variables are provided in an internal Biometrics document that specifies the programming rules including the precision for derived variables.

All individual subject data for those randomized or dosed with any amount of study drug will be presented in data listings.

Continuous variables will be summarized using the following descriptive summary statistics: the number of subjects (n), mean, SD, standard error (SE), median, minimum value (min), and maximum value (max). SE may not be reported for safety summary tables.

Categorical variables will be summarized using counts and percentages. Percentages will be presented to 1 decimal place.

Baseline value, unless otherwise specified, will be defined as the most recent non-missing measurement (scheduled or unscheduled) collected before the first dose of study drug on Day 1 of the Treatment Period. For ECG, baseline will be defined as the most recent non-missing measurement (or the average of triplicate measurements, if the most recent non-missing measurement is obtained in triplicate), before the first dose of study drug on Day 1 of the Treatment Period.

Absolute change from baseline will be calculated as postbaseline value – baseline value.

Relative change from baseline will be calculated as (postbaseline value – baseline value)/baseline value.

Treatment-emergent (TE) period for Parts 1 and 3 will be from the first dose date of study drug in the Treatment Period until 28 days after the last dose date of study drug or end of study date (based on end of study visit in CRFs), whichever occurs first.

For Part 2, the TE period will be defined separately for the Run-In Period, and the Treatment Period:

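### For Part 2, the SAP's sweat chloride fallback baseline is the screening value from before the run-in, although an on-TEZ/IVA value is scheduled at Day -14

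*SAP*

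**What the plan says.** SAP Appendix B, Derived Variables, item 5 sets the sweat chloride baseline. Day 1 samples finished up to 30 minutes after the first dose are accepted. Then: "If Day 1 value is unavailable or invalid, screening value will qualify as baseline". No part is named, and Day -14 is not mentioned.

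The general definition in SAP 8.1 is the "most recent non-missing measurement (scheduled or unscheduled) collected before the first dose of study drug on Day 1 of the Treatment Period". Protocol 12.3.1 is equivalent. Both give way to a more specific rule. The efficacy window rules in Appendix B (rule 2.a.i) add: "If there are no measurements at the scheduled visit, then the measurement closest to the target day will be used".

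On the design, Protocol 9.1.2 says the Part 2 run-in is "designed to establish a reliable on-treatment (TEZ/IVA) baseline for the Treatment Period", and Protocol 9.3.1 repeats this. Protocol Table 3-2 and SAP Table 11-2 schedule Part 2 sweat chloride at Screening, Day -14 and Day 1, with none at Day -28.

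**The concern.** The fallback takes its value from the wrong treatment state. A Part 2 subject without a usable Day 1 sample would be measured against a value from before the run-in, while a scheduled value on TEZ/IVA goes unused. Any fall in sweat chloride produced by TEZ/IVA during the run-in would then be counted in Period 1. In the control arm, which simply continues TEZ/IVA, it would look like a new response.

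The baseline feeds the Part 2 within-group and between-group MMRM estimates (SAP 8.3.5.2), where it is also a covariate, the Day 29 waterfall plot, and the baseline characteristics table (SAP 8.2.2). Because item 5 and SAP 8.1 can be read as choosing different values, two programmers working from the SAP could derive different baselines for the same subject.

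**Working it through.** The plan states no figure on this point, so the check is first of the rules and then of the possible size.

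**Which value each rule selects in Part 2 when Day 1 is unusable**

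| Rule | Value selected | Treatment state |
|---|---|---|
| Appendix B item 5, read literally | Screening, Days -56 to -29 | Before the run-in |
| SAP 8.1 / Protocol 12.3.1 | Day -14 visit, Days -15 to -3 (or a later unscheduled value) | On TEZ/IVA |
| Appendix B rule 2.a.i, applied to the pre-dose baseline window | Day -14 visit | On TEZ/IVA |

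By schedule, the Day -14 value is 14 days (-15 minus -29) to 53 days (-3 minus -56) later than the screening value. In Parts 1 and 3 no sweat chloride is scheduled between Screening and Day 1, so the rules agree there unless an unscheduled value exists.

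**Time on TEZ/IVA at the Day -14 visit.** The first run-in dose is at Day -28 ± 1. The minimum is -15 - (-27) = 12 days and the maximum is -3 - (-29) = 26 days. Protocol 9.3.2 reports that in two earlier studies improvements in sweat chloride and ppFEV₁ "were observed during the first week of dosing, with most of the effect observed within 14 days".

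**Possible size**

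- From the documents: about 27 subjects randomized 1:2, so 9 control and 18 TC-high.
- Assumed, because the documents give no figures: run-in effect e = 5 to 15 mmol/L (screening minus on-TEZ/IVA level); fraction p = 1 to 5% with no usable Day 1 value; slope b = 0.5 to 0.8 of the post-baseline value on baseline.

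Adjusted means are taken at the overall baseline mean. Replacing one subject's baseline by a value e higher raises that arm's baseline mean by e/n and the overall mean by e/27. With b held fixed, the arm's adjusted change moves by -b·e/n - (1-b)·e/27:

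- One affected control (n = 9): -e(1+2b)/27, from -5(2.0)/27 = -0.37 to -15(2.6)/27 = -1.44 mmol/L.
- One affected TC-high subject (n = 18): -e(2+b)/54, from -5(2.5)/54 = -0.23 to -15(2.8)/54 = -0.78 mmol/L.
- In either case the other arm moves by -(1-b)e/27.

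If each subject is affected with probability p regardless of arm:

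- Expected number affected: 27p = 0.27 to 1.35.
- Expected shift in each arm: -b·p·e - (1-b)·p·e = -p·e, from -0.01 × 5 = -0.05 to -0.05 × 15 = -0.75 mmol/L.
- Expected between-arm shift: zero, since both arms move by -p·e.
- Chance SD of the between-arm shift: b·e·√[p(1-p)(1/9 + 1/18)], from 2.5 × √(0.0099/6) = 0.10 to 12 × √(0.0475/6) = 1.07 mmol/L.

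A simulated two-visit MMRM with unstructured covariance (assumed baseline SD 12, subject SD 9, residual SD 8) agrees. With one affected subject the shift is -0.37 to -1.40 in control and -0.23 to -0.76 in TC-high. With random p, the mean between-arm shift stays within ±0.02 and its SD is 0.12 to 1.09. The simulation confirms the algebra, not the assumed inputs.

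**The case against.** The strongest reply is that item 5 only lists admissible values. Its verb is *qualify*, so screening may merely be eligible, with SAP 8.1 still choosing the most recent value, Day -14. This reading is possible, and because the general definitions allow exceptions there is no formal contradiction. But the SAP does not say this is the intended reading, and Screening is a separate named visit. SAP 8.1 mentions an internal programming document, but the reader cannot see it or assume that it settles the matter.

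The second reply is that the trigger is rare and harmless, and much of this stands:

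- One valid arm is enough (SAP 8.3.5), the Day 1 sample may be taken on Day -1 (Table 3-2, footnote o), and inclusion criterion 5 requires a valid sweat sample at screening.
- Baseline samples are taken predose or at most 30 minutes after the first dose, so failure should not depend on treatment.
- Every input to the size is assumed. Protocol 9.3.2 does not give the genotypes behind its 14-day remark, so applying it to F/F subjects is an inference.
- The run-in effect may be near zero for someone screened on a modulator. Part 2 subjects may come from Study 661-110 (Protocol 9.1.5), and Protocol 9.1.1.3 mentions the four-week washout before Day 1 only for Parts 1 and 3.

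Against this, a screening value can be older than it looks. The window may be extended by two to four weeks (Protocol 9.1.1.3), and sweat chloride is not repeated at rescreening (Protocol 9.1.1.2).

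**Conclusion.** The concern holds as a minor but real defect. Followed literally, item 5 gives an affected Part 2 subject a baseline in the wrong treatment state, against the stated purpose of the run-in; read the other way, it is ambiguous where a derivation rule should not be.

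Under the assumed ranges, about one subject or fewer would be affected, each arm's adjusted fall would be overstated by less than 1 mmol/L in expectation, and the expected between-arm bias is zero. What remains is chance imbalance in arms of 9 and 18, and an error of up to the full run-in effect in an affected subject's own change. The zero between-arm bias rests on missingness being unrelated to treatment. The point is confined to Part 2 sweat chloride, a secondary endpoint, and its baseline summary. It is an optional improvement.

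**What to change.** In Appendix B item 5, limit the screening fallback to Parts 1 and 3 and add for Part 2:

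> If the Day 1 value (including a permitted predose Day -1 sample) is unavailable or invalid, baseline is the most recent valid value collected after the first run-in dose of TEZ/IVA and before the first Day 1 dose (Day -14 or unscheduled). The screening value is used only if there is none, and is flagged.

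A shorter alternative is to state that Part 2 follows SAP 8.1, but that leaves any use of a screening value unflagged.

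The cost is one SAP sentence. Day -14 sweat chloride is already scheduled, so no new data are needed and no subject leaves the model. The one downside is that a Day -14 value can be about two weeks older than a Day 1 value.

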
Appendix C: Imputation Rules for Missing Prior/Concomitant Medication Dates

Imputation rules for missing or partial medication start/stop dates are defined below:

1. Missing or partial medication start date:
 - a. If only DAY is missing, use the first day of the month.
 - b. If DAY and Month are both missing, use the first day of the year.
 - c. If DAY, Month and Year are all missing, use a date before the first dose date (in practical, use Jan. 01, 2000 to impute).
2. Missing or partial medication stop date:
 - a. If only DAY is missing, use the last day of the month.
 - b. If DAY and Month are both missing, use the last day of the year.
 - c. If DAY, Month and year are all missing, assign ‘continuing’ status to stop date (in practical, use Dec. 31, 2050 to impute).

In summary, the prior, concomitant, or post categorization of a medication is described below.

Table 11-5 Prior, Concomitant, and Post Categorization of a Medication in Parts 1 and 3

Medication Start Date	Medication Stop Date		
	< First Dose Date of Study Drug	≥ First Dose Date and ≤ End Date of TE Period	> End Date of TE Period
< First dose date of study drug	P	PC	PCA
≥ First dose date and ≤ End date of TE period	-	C	CA
> End date of TE period	-	-	A

P: Prior; C: Concomitant; A: Post

Table 11-6 Prior, Concomitant, and Post Categorization of a Medication in Part 2

Medication Start Date	Medication Stop Date			
	< First Dose Date of Run-in TE Period	≥ First Dose Date and ≤ End Date of Run-in TE Period	≥ First Dose Date and ≤ End Date of Treatment TE Period	> End Date of Treatment TE Period
< First dose date of Run-in TE period	P	PC1	PC1C2	PC1C2A
≥ First dose date and ≤ End date of Run-in TE Period	-	C1	C1C2	C1C2A
≥ First dose date and ≤ End date of Treatment TE Period	-	-	C2	C2A
> End date of Treatment TE Period	-	-	-	A

P: Prior; C1: Concomitant during the Run-in Period; C2: Concomitant during the Treatment Period; A: Post

